**Synopsis****Protocol Title:**

A Randomized, Double-Blind, Placebo-Controlled, Parallel-Group Study to Evaluate the Efficacy and Safety of ETX-018810 in Subjects with Lumbosacral Radicular Pain

**Short Title:**

Efficacy and Safety of ETX-018810 for the Treatment of Lumbosacral Radicular Pain

**Rationale:**

ETX-018810 is a new chemical entity that is under development as a non-opioid treatment for chronic pain syndromes. ETX-018810 is a prodrug of palmitoylethanolamide (PEA), an endogenous bioactive lipid that has shown efficacy in a broad range of nonclinical inflammatory and neuropathic pain models and in clinical trials in chronic pain indications, including lumbosacral radicular pain (LSRP).

The existing clinical validation of the efficacy of PEA, the safety and tolerability of ETX-018810 in nonclinical toxicology studies and in a Phase 1 single- and multiple-, ascending-dose study, and a post hoc analysis, which confirms the clinical efficacy of PEA on pain in patients with low back pain, support its potential as a treatment for LSRP, a pain condition for which there is high unmet medical need due to the suboptimal efficacy and unacceptable adverse effects of current therapies. This study is designed to evaluate the efficacy, safety, and tolerability of ETX-018810 for the treatment of LSRP.

**Objectives and Endpoints:**

The study objectives and endpoints are summarized in [Table S-1](#).

**Table S-1: Study Objectives and Endpoints**

Objectives	Endpoints
Primary	

 
• To evaluate the efficacy of ETX-018810 for the treatment of lumbosacral radicular pain (LSRP)
 
	
 
• Change from baseline to Week 4 in the weekly average of the daily pain score on the 11-point Pain Intensity Numerical Rating Scale (PI-NRS)
 

Secondary	

 
• To evaluate the efficacy of ETX-018810 on additional pain measures and assessments of disability
 
	
Secondary efficacy endpoints in pain:
 
 
• Response rate, defined as a <math>\geq 50\%</math> reduction from baseline to Weeks 1, 2, 3, and 4 in the weekly average of the daily pain score
 
• Response rate, defined as a <math>\geq 30\%</math> reduction from baseline to Weeks 1, 2, 3, and 4 in the weekly average of the daily pain score
 
• Change in the weekly average of the daily pain score from baseline to Weeks 1, 2, and 3
 
• Change from baseline to Week 4 for worst pain
 
 
Secondary efficacy endpoints:
 
 
• Response rate on the Patient Global Impression of Change (PGIC) scale at Week 4, defined as the proportion of subjects who are “much improved” or “very much improved”
 
• Response rate on the Clinical Global Impression of Change (CGIC) scale at Week 4, defined as the proportion of subjects who are “much improved” or “very much improved”
 
• Change in the weekly average of the daily sleep score on the Daily Sleep Interference Scale (DSIS) from baseline to Weeks 1, 2, 3, and 4
 
• Change from baseline to Week 4 in the Brief Pain Inventory (BPI)
 
• Change from baseline to Week 4 in the Roland-Morris Disability Questionnaire
 
• Amount of rescue mediation used (dosage/day)
 

 
• To investigate the safety and tolerability of ETX-018810 in subjects with LSRP
 
	
 
• Nature, frequency, and severity of nonserious treatment-emergent adverse events (TEAEs) and serious adverse events (SAEs)
 
• Frequency of discontinuations due to TEAEs or death
 

**Table S-1: Study Objectives and Endpoints (Continued)**

Objectives	Endpoints

 
To characterize the pharmacokinetics (PK) of ETX-018810 in subjects with LSRP
 
	
 
Plasma concentrations and plasma PK parameters (maximum observed drug concentration [<math>C_{max}</math>]) over the first 5 hours after dosing and area under the plasma concentration-time curve computed up to 5 hours after dosing [<math>AUC_{0-5h}</math>] of palmitoylethanolamide (PEA)
 

1. Participation in the PK component of the study is optional.
2. Subjects will record the PI-NRS score that represents their overall pain in the index leg (most painful leg) over the last 24-hour period in the electronic diary (eDiary) once daily in the evening (when they take their second daily dose of investigational product).
3. Subjects will record their DSIS score in the eDiary, once daily in the morning (when they take their first daily dose of investigational product).
4. Subjects will record their worst pain via question 3 of the BPI on Days 1 and 28.
5. Subjects will record rescue medication (acetaminophen) use in the eDiary once daily in the evening (when they take their second daily dose of investigational product).

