Subjects will be contacted by telephone to review their status at the end of Week 2 and will report to the clinic for an end-of-treatment (EOT) visit at the end of Week 4. A final posttreatment follow-up telephone contact will be made 1 week after the last dose of investigational product (Week 5) to inquire about adverse events (AEs) and concomitant medication use. Subjects who discontinue from the study before completing the planned 4 weeks of treatment will undergo an early termination visit, which will include the evaluations that are scheduled for the Week 4 visit. If an ongoing automated review of the eDiary reveals that the subject is not complying with study procedures, site personnel will contact the subject to discuss any issues in an effort to improve compliance.

Subjects will take their first dose of investigational product in the clinic on Day 1 (baseline),  

Blood specimens for plasma concentrations of PEA and for calculation of plasma pharmacokinetic (PK) parameters of PEA will be obtained before  

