**Number of Subjects:**

Approximately 203 subjects will be screened to achieve a minimum of 122 randomized subjects (61 per treatment group). Subjects for whom diary data is unavailable due to technical issues may be replaced.

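### Do Cmax and AUC0-5h of PEA, an endogenous lipid, fail the PK objective for ETX-018810 because no correction for pre-dose PEA is shown?

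*Combined protocol and SAP*

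**What the plan says.** The PK objective in Table S-1 (Continued) reads "To characterize the pharmacokinetics (PK) of ETX-018810 in subjects with LSRP". Its endpoint is "Plasma concentrations and plasma PK parameters (maximum observed drug concentration", taken over the first 5 hours after dosing, together with "area under the plasma concentration-time curve computed up to 5 hours after dosing". The row closes by naming PEA as the substance measured. Note 1 to the table adds: "Participation in the PK component of the study is optional".

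The synopsis Rationale explains the choice of analyte: "ETX-018810 is a prodrug of palmitoylethanolamide (PEA), an endogenous bioactive lipid".

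Overall Design says "Subjects will take their first dose of investigational product in the clinic on Day 1 (baseline", and that text then breaks off. The sampling sentence is "Blood specimens for plasma concentrations of PEA and for calculation of plasma pharmacokinetic (PK) parameters of PEA will be obtained before", and it stops there. The synopsis section headed Statistical Analysis Plan gives a general rule for summarising continuous data. It contains no PK-specific text.

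**The concern.** The objective names the drug, while the parameters are those of a substance the body makes for itself. Subjects have PEA in plasma before any dose, and a placebo subject would have a non-zero AUC0-5h without any exposure to ETX-018810. Nothing in the visible endpoint row subtracts the pre-dose level.

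If total PEA were read as exposure produced by ETX-018810, Cmax would carry the endogenous level once and AUC0-5h would carry it for all 5 hours. Exposure would then be overstated, by more for AUC than for Cmax. A correction by each subject's value before the first dose is a familiar remedy. It would cost little if that sample is already drawn.

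**Working it through.** The plan states no PK figure, so there is nothing to reproduce. The check has three parts.

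**1. The texts side by side.**

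- *Analyte.* Both the endpoint row and the sampling sentence name PEA. The Rationale says the drug is a prodrug of PEA. Describing a prodrug through the moiety it releases is a normal choice, and the label tells the reader what was measured.
- *Correction.* A synopsis endpoint row lists parameters. Derivation rules such as baseline subtraction are not normally set out there, so its silence says little. The places to look are the sampling description and the PK analysis text. The first is cut immediately after the word introducing the pre-dose time, and the second is not visible at all. Text lost in this way cannot be counted as missing from the plan.
- *Pre-dose sample.* The first dose is taken in the clinic on Day 1, so a sample before it is plausible. The visit cannot be read. Because plasma concentrations are themselves an endpoint, such a sample would put each subject's own PEA level among the reported data.

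**2. Possible size (all values assumed).** Let C0 be a constant endogenous level, r = C0 / drug-derived Cmax, and k = the mean-to-peak ratio of drug-derived concentration over 0–5 h, taken as 0.5 to 0.2.

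- Excess of total over drug-derived Cmax = r.
- Excess of total over drug-derived AUC0-5h = 5·C0 / (5·k·Cmax) = r/k.

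| r | Cmax excess | AUC0-5h excess, k = 0.5 to 0.2 |
|---|---|---|
| 0.01 | 1% | 2% to 5% |
| 0.10 | 10% | 20% to 50% |
| 0.50 | 50% | 100% to 250% |

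A separate calculation used an assumed one-compartment oral curve (ka 2/h, ke 0.5/h). With R = total Cmax / C0, the endogenous share of Cmax is 1/R:

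- R = 1.5: 67% of Cmax and 78% of AUC0-5h
- R = 5: 20% and 31%
- R = 20: 5% and 9%

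The two calculations agree that the effect could be negligible or dominant. Nothing in the documents narrows the range.

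**3. Is subtraction better whatever C0 is?** Let E be the endogenous level at the time that matters and P the pre-dose value. The total is off by E and the corrected value by |E − P|, so correction is closer when 0 < P < 2E. With E and P independent, lognormal and of equal mean:

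- CV 20% each: Φ(ln 2 / √(2·ln 1.04)) = 0.993
- CV 40% each: Φ(ln 2 / √(2·ln 1.16)) = 0.898

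Root mean square error in units of C0, total against corrected:

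- CV 20%: √1.04 = 1.02 against √0.08 = 0.28
- CV 40%: √1.16 = 1.08 against √0.32 = 0.57

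This arithmetic is sound, but it takes drug-derived exposure as the target. Total PEA is a valid measure in its own right, and against that target nothing needs subtracting. The result also needs a measurable pre-dose value, and no assay limit is given.

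Keeping negative corrected values is not a complete remedy either. For one post-dose sample with no drug-derived PEA and 20% CV in each sample, setting negatives to zero gives a mean of 0.2·√2·0.399 = +0.113·C0 instead of 0, so keeping them removes that bias. Cmax, however, is a maximum over several samples. With 4 to 8 independent lognormal samples (numbers assumed, CV 20%), simulation gives a mean corrected Cmax of +0.21 to +0.31·C0 with negatives kept. Correction still beats the total there, but it leaves an upward bias in one of the two parameters.

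**The case for a change.** The strongest case for the concern is that it does not need the hidden text. The visible row defines total PEA, the objective names ETX-018810, and the Rationale says PEA is endogenous. On that reading the parameters do not isolate what the objective names. Reporting corrected values beside the totals would cost one subtraction and remove nothing.

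Two parts of this stand. The objective is loosely worded: the pharmacokinetics of PEA after ETX-018810 would be more exact. And if the full plan has no correction, and a sample before the first dose exists, corrected values would be a sensible supplement.

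Neither part shows a fault. The wording misleads nobody about the analyte, because the same row names it. The supplement depends on two conditions that cannot be checked: that no correction is specified elsewhere, and that the pre-dose sample precedes the first dose rather than following repeated dosing, when it may hold drug-derived PEA. Placebo samples are no sure substitute. The plan has a "minimum of 122 randomized subjects (61 per treatment group"), but PK is optional, and the number of placebo subjects sampled is not given.

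**Conclusion.** The concern does not hold. Followed as written, the plan yields correctly labelled concentrations, Cmax and AUC0-5h of the moiety the prodrug releases. That no endogenous correction is planned cannot be shown from text that is cut where the sampling scheme would appear and that contains no PK analysis. At most a derivation detail is unseen, and a PK analyst would be expected to settle it sensibly.

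The possible effect, 1% to 50% on Cmax and 2% to 250% on AUC0-5h, rests wholly on an assumed endogenous level and an assumed profile shape, so it cannot establish that anything is wrong. The PK component is secondary and optional. No sample size, error rate, or efficacy or safety conclusion in the visible text depends on it. The one point that needs no assumption is the wording of the objective, and that is editorial.

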### Overall Design:

This is prospective, Phase 2, multicenter, randomized, double-blind, placebo-controlled, parallel-group study to evaluate the efficacy, safety, and tolerability of ETX-018810 in male and female subjects aged  $\geq 18$  and  $\leq 75$  years with a diagnosis of LSRP, with an onset  $\geq 3$  months before screening, and at least moderate pain intensity on the Patient Global Impression of Severity (PGI-S) scale. The study will include a screening period (maximum of 4 weeks), a 4-week treatment period, and a 1-week posttreatment follow-up period. Each subject will participate in the trial for up to approximately 9 weeks.

After providing written informed consent, potential study subjects will be screened for study eligibility during the maximum 4-week screening period. Subjects who meet the study entry criteria will be trained in the use of the electronic diary (eDiary) and in the completion of the Pain Intensity Numeric Rating Scale (PI-NRS), completion of the Daily Sleep Interference Scale (DSIS), and documentation of rescue medication use (acetaminophen) and will be instructed to discontinue any prohibited medications at the screening visit.

Subjects will record their PI-NRS score over the last 24 hours once daily in the evening, their DSIS score once daily in the morning, and their rescue medication use once daily in the evening in the eDiary from screening until the baseline/Day 1 visit. Subjects will record their average pain intensity in their worst affected limb, as identified at screening, over the last 24 hours for their pain due to LSRP (pain in relation to the symptomatic nerve root(s), which is perceived in the lower limb).

The values that are recorded for the PI-NRS and DSIS on the last 7 days before the baseline/Day 1 visit will be used to determine the baseline scores. Only the intensity of pain due to LSRP will be used to determine eligibility. Subjects whose average pain intensity over these

[REDACTED]

7 days meets the study-specified threshold, who completed the PI-NRS and DSIS in the eDiary on at least 5 of the 7 days before the baseline/Day 1 visit, and who continue to meet all other study eligibility criteria will be enrolled in the study. The baseline assessment of eligibility will be made using a computerized screening algorithm on the basis of the information that is recorded in the eDiary. The investigator, site team, and study monitors will be blinded to the screening algorithm. The investigator/site staff will be informed as to whether the algorithm classifies the subject as eligible or ineligible and will inform the subject if he/she is eligible to continue in the study. Subject will be randomized to receive double-blind treatment with ETX-018810 1000 mg or placebo twice daily (BID) for 4 weeks at the baseline/Day 1 visit. Subjects will be trained on scoring of their pain intensity at the baseline visit.

Subjects will continue to use the eDiary to record their LSRP pain score, as defined above, over the last 24 hours on the PI-NRS (once daily in the evening when they take their second daily dose of investigational product), their sleep interference as a result of their LSRP on the DSIS (once daily in the morning when they take their first daily dose of investigational product), and rescue medication use (once daily in the evening when they take their second daily dose of investigational product) throughout the 4-week double-blind treatment period. Subjects will be allowed to take acetaminophen at a dose of up to 2600 mg/day for up to 3 consecutive days, but for no more than a total of 7 days, for non-LSRP-related pain (headache, toothache, etc) or for breakthrough pain due to LSRP.

Subjects will be contacted by telephone to review their status at the end of Week 2 and will report to the clinic for an end-of-treatment (EOT) visit at the end of Week 4. A final posttreatment follow-up telephone contact will be made 1 week after the last dose of investigational product (Week 5) to inquire about adverse events (AEs) and concomitant medication use. Subjects who discontinue from the study before completing the planned 4 weeks of treatment will undergo an early termination visit, which will include the evaluations that are scheduled for the Week 4 visit. If an ongoing automated review of the eDiary reveals that the subject is not complying with study procedures, site personnel will contact the subject to discuss any issues in an effort to improve compliance.

Subjects will take their first dose of investigational product in the clinic on Day 1 (baseline),  

Blood specimens for plasma concentrations of PEA and for calculation of plasma pharmacokinetic (PK) parameters of PEA will be obtained before  

**Disclosure Statement:**

This is a double-blind, parallel-group study of ETX-018810 and placebo in subjects with LSRP. Treatment assignments will be blinded to the subjects, investigators and other study personnel, and all sponsor personnel that are involved in the conduct of the study or in the analysis of the study results. The subjects and investigators will be blinded to the study-specified baseline criteria that are necessary for randomization into the study.

**Number of Subjects:**

Approximately 203 subjects will be screened to achieve a minimum of 122 randomized subjects (61 per treatment group). Subjects for whom diary data is unavailable due to technical issues may be replaced.

**Treatment Groups and Duration:**

Each subject will participate in the study for approximately 9 weeks, including a screening period of up to 4 weeks; a 4-week, double-blind treatment period; and a 1-week posttreatment follow-up period. Subjects will be randomized in a 1:1 ratio to receive 1000 mg of ETX-018810 or placebo BID for 4 weeks.

**Statistical Analysis Plan:**

The analysis populations were defined as:

- Safety Population - All subjects who received at least 1 dose of study treatment.
- Intent-to-treat (ITT) Population - All randomized subjects who received at least 1 dose of study treatment.
- Modified intent-to-treat (mITT) Population - All subjects in the ITT population who had at least 4 postbaseline measurements for the Pain Intensity Numeric Rating Scale (PI-NRS) in the eDiary.

The mITT population was used for the primary analysis of the primary efficacy endpoint and for all other eDiary efficacy endpoints; the ITT population was used for the analyses of the secondary efficacy endpoints. The safety population was used for the safety analyses.

Continuous data were summarized using descriptive statistics (e.g., mean, standard deviation), and categorical data were summarized using counts and percentages.

For the PI-NRS and DSIS (for which scores were completed daily in the eDiary), the weekly average was the mean of the non-missing scores for the 7-day period; the weekly average was calculated if at least one score was recorded for the week.

The treatment comparison for the change from baseline at Week 4 was estimated using a Mixed Model Repeated Measures (MMRM), which included the baseline score as a covariate; treatment group, visit (week), and the treatment-by-visit (week) as fixed effects; and a repeated structure that acknowledged the visits within a subject using an unstructured covariance structure. The Kenward-Rogers (1997) approximation was used to estimate the denominator degrees of freedom. The estimate, standard error, 90% CI, and associated p-value (2-sided) were presented.

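### The primary MMRM drops treated subjects with one to three post-baseline pain scores, although the plan's own one-score weekly mean makes their data usable

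*Combined protocol and SAP*

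**What the plan says.** All the rules at issue stand in the synopsis, under Statistical Analysis Plan.

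- ITT: "All randomized subjects who received at least 1 dose of study treatment".
- mITT: "All subjects in the ITT population who had at least 4 postbaseline measurements for the Pain Intensity Numeric Rating Scale (PI-NRS) in the eDiary".
- Use of the populations: "The mITT population was used for the primary analysis of the primary efficacy endpoint and for all other eDiary efficacy endpoints"; then, in the same sentence, "the ITT population was used for the analyses of the secondary efficacy endpoints".
- Weekly mean for the PI-NRS and DSIS: "the weekly average was calculated if at least one score was recorded for the week".
- Primary model: an MMRM over the four weeks with unstructured covariance and the baseline score as covariate.

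Three other places bear on the point. Table S-1, footnote 3, describes the sleep score as a separate entry: "Subjects will record their DSIS score in the eDiary, once daily in the morning". The pain score is entered in the evening. Overall Design admits only subjects "who completed the PI-NRS and DSIS in the eDiary on at least 5 of the 7 days before the baseline/Day 1 visit", and adds follow-up during treatment: "If an ongoing automated review of the eDiary reveals that the subject is not complying with study procedures, site personnel will contact the subject".

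**The concern.** Membership of the primary analysis set depends on how many diary entries a subject makes after randomization, which treatment could affect. The model does not need this restriction. One score gives a weekly mean, and one weekly mean is enough for a subject to contribute to the MMRM.

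Nor does the threshold secure the Week 4 endpoint. Four scores in Week 1 and nothing later qualify a subject. Three scores in Week 4, which give a valid Week 4 mean under the plan's own rule, do not. Because evening pain entries are counted but the set also governs the morning DSIS, usable sleep data can be lost as well.

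If subjects who do badly early stop their diaries more often in one arm, removing them shifts the treatment contrast. The population sentence has a further problem: it places the eDiary secondary endpoints (responder rates, change at Weeks 1–3, DSIS, rescue use) under both mITT and ITT.

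**Working it through.** **Who is affected.** "Measurements" in the mITT definition is read here as daily scores.

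| Post-baseline PI-NRS scores | Weekly means available | Usable by the MMRM | In mITT |
|---|---|---|---|
| 0 | 0 | no | no |
| 1–3 | 1 to 3 | yes | no |
| 4 or more | 1 to 4 | yes | yes |

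The baseline covariate exists for every properly enrolled subject because of the 5-of-7-day entry rule. Subjects with no scores are absent under either rule and are not at issue. Only the middle row is.

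**What kind of subject has one to three scores.** One evening score per day over four weeks gives about 28 possible scores. Take the entry minimum, 5/7, as the chance of an entry each evening, and assume evenings are independent. Both are assumptions; real missed entries may cluster.

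- Diary kept for all 28 evenings: P(3 or fewer) = Σ C(28,k)(5/7)^k(2/7)^(28−k), k = 0 to 3, = 3.1 × 10⁻¹¹. At an entry rate of 0.5: (1 + 28 + 378 + 3276)/2²⁸ = 1.4 × 10⁻⁵.
- Entries stop after 3 evenings: P(1–3) = 1 − (2/7)³ = 0.98. After 4: 1 − (2/7)⁴ − (5/7)⁴ = 0.73. After 5, 7 and 10 evenings: 0.44, 0.11 and 0.01.

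Scattered missed evenings therefore do not explain such low counts. The filter mainly removes subjects whose entries stop within about the first week, most of them in the first five evenings.

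**Size of the effect.** The only input from the documents is 61 per arm (Number of Subjects). Assumed:

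- SD 2.0, so SE of the difference = 2.0 × √(2/61) = 0.362
- regression slope of Week 4 on Week 1, 0.4–0.8
- excluded subjects 0.5–1.0 points worse at Week 1 than retained subjects
- all their scores in Week 1

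With a active and p placebo subjects excluded, the expected shift in the active-minus-placebo contrast (ITT minus mITT) is

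((a − p)/61) × slope × gap.

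| Excluded, active vs placebo | Smaller inputs (0.4 × 0.5) | Larger inputs (0.8 × 1.0) | In SE |
|---|---|---|---|
| equal | 0 | 0 | 0 |
| 2 vs 1 | 1/61 × 0.2 = 0.003 | 1/61 × 0.8 = 0.013 | 0.01–0.04 |
| 4 vs 1 | 3/61 × 0.2 = 0.010 | 3/61 × 0.8 = 0.039 | 0.03–0.11 |
| 1 vs 4 | −0.010 | −0.039 | 0.03–0.11, opposite sign |

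A positive shift means the four-score set made active look better than the fuller set does. Simulation (4,000 trials per setting) agrees: mean shifts of 0.009 and 0.040 for 4 vs 1, −0.009 and −0.039 for 1 vs 4, and within 0.002 of 0 for equal counts. In a single trial chance can move it either way: for 4 vs 1 at the larger inputs, 95% of shifts lay between −0.08 and +0.16 points.

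**A harsher case.** A second simulation (2,000 trials; SD 2, correlation 0.7 between weeks, true effect −1.0) let only subjects with no improvement at Week 1 stop early. The estimate without and with the exclusion was:

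- −1.00 and −1.08 with on average 3.2 active and 1.0 placebo subjects excluded
- −1.00 and −1.09 with 4.7 and 2.1
- −1.01 and −1.15 with 4.7 and 0
- −1.01 and −1.00 with 1.6 and 2.1

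The largest difference, 0.147 before rounding, needs a Week 1 gap of about 0.147/(0.7 × 4.744/61) = 2.7 points and no exclusions on placebo.

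**The case against.** The strongest objections concern weight and remedy; the logic is not in dispute.

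- *The fix also conditions on post-randomization data.* It does require one value, but a subject with none adds nothing to the model under any rule, whereas the four-score rule removes subjects the model would use. It remains true that if early stopping is not missing at random, neither population removes the bias.
- *Stopping may be technical.* The Number of Subjects section allows replacement of subjects whose diary data are unavailable for technical reasons, and such losses need have nothing to do with treatment. This stands as an alternative cause, and no figure in the documents shows treatment-related stopping. But replacing a subject does not take that person out of the ITT set or undo the filter.
- *The probability for a full 28 days is too precise.* It rests on independence and on the entry minimum as a constant rate. It shows only that sporadic missing evenings are not the explanation.
- *Three scores only in Week 4 is a contrived case.* It would be rare. It shows that the threshold is not tied to the endpoint. Nothing shows that DSIS data would in fact be lost.
- *An ITT analysis may exist elsewhere.* Only a synopsis-level plan is available, and it speaks of the primary analysis, which leaves room for others. If one is specified, it should be cited.
- *The population overlap is drafting.* Largely so: the specific eDiary clause probably governs, leaving ITT for PGIC, CGIC, BPI and Roland-Morris. The text does not say this.

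**Conclusion.** The concern holds. The plan's own rules make subjects with one to three post-baseline scores usable, then exclude them without a stated reason. That conclusion comes from reading the rules against each other and needs no outside figure.

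The consequence is probably small. The entry rule and the eDiary follow-up should keep exclusions few, and the expected shift is at most 0.039 points (0.11 SE) in the main scenarios. It approaches 0.15 points only with much larger gaps and one-sided exclusions, and it vanishes when exclusions are balanced and alike. Apart from 61 per arm, every input to these sizes is assumed, and the direction cannot be known from the documents. This is a cheap improvement, not a threat to the trial. Whether an ITT analysis of the primary endpoint is planned outside the synopsis remains open.

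**What to change.** 1. Run the primary MMRM and the other eDiary analyses on all ITT subjects with at least one post-baseline value for that endpoint. Keep the four-score mITT as a labelled sensitivity analysis.
2. If the data are already unblinded (the section is written in the past tense), do not swap the two. Keep mITT as primary and add the ITT analysis as the labelled sensitivity analysis.
3. Report by arm the number of treated subjects with 0 and with 1–3 post-baseline PI-NRS scores.
4. Replace the population sentence with one named population for each endpoint, so that the eDiary secondary endpoints no longer fall under two.

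Cost: minor SAP wording, one re-run of existing code and one count table. No new data or patients are needed. The estimate may move slightly in either direction.

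### Does letting one diary score stand as a weekly average, even at Week 4, undermine the primary analysis?

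*Combined protocol and SAP*

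**What the plan says.** All of this comes from the synopsis. Table S-1 defines the primary endpoint: "Change from baseline to Week 4 in the weekly average of the daily pain score on the 11-point Pain Intensity Numerical Rating Scale". Its secondary pain endpoints include 30% and 50% responder rates, each defined as a "reduction from baseline to Weeks 1, 2, 3, and 4 in the weekly average of the daily pain score".

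The Statistical Analysis Plan section builds the weekly value simply: "the weekly average was the mean of the non-missing scores for the 7-day period", and "the weekly average was calculated if at least one score was recorded for the week". The rule serves both PI-NRS and DSIS and makes no exception for Week 4. The only other post-baseline threshold is membership of the mITT population, the primary analysis set: ITT subjects who "had at least 4 postbaseline measurements for the Pain Intensity Numeric Rating Scale (PI-NRS) in the eDiary". That count runs over the whole treatment period.

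Three other provisions bear on diary completeness:

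- At entry, Overall Design admits subjects "who completed the PI-NRS and DSIS in the eDiary on at least 5 of the 7 days before the baseline/Day 1 visit".
- During treatment, the same section provides an ongoing automated review of the diary, with site contact when a subject is not complying.
- Number of Subjects adds: "Subjects for whom diary data is unavailable due to technical issues may be replaced".

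None of the three sets a minimum number of days for a post-baseline weekly average.

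**The concern.** The baseline mean needs 5 of 7 days, while the Week 4 mean can rest on 1 of 7, so the two ends of the change score can differ sharply in precision. The MMRM as described does not weight a weekly mean by the number of days behind it. The mITT threshold offers no protection at Week 4, and for DSIS there is no count of its own at all.

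Three things could be at stake: noise in the primary comparison, misclassified responders, and bias in the treatment difference. Bias would arise if subjects in one arm tended to stop recording when they got worse, leaving a single unrepresentative score. Without diary-day counts by arm, a reader could not see that pattern.

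**Working it through.** **The gap is real.** Exactly 4 scores can be spread over 4 weeks in 35 ways. Ten of these leave exactly one score in Week 4 (1-1-1-1 or 3-0-0-1, for example), and all ten satisfy the mITT rule.

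**Inputs.** From the documents: 61 per arm, 7 possible days per week, and a minimum of 1. The supplied text gives no SD, effect size, alpha, power or share of sparse weeks, so the sample size cannot be reproduced. Assumed: daily within-subject SD 1.2 (variance 1.44); between-subject SD of the weekly mean 1.8 (variance 3.24); lag-1 daily correlation 0 to 0.5; 5% to 20% of Week 4 values from one day; 80% power with complete weeks; two-sided 5%.

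**Precision.** The within-subject variance of a 7-day mean is 1.44/7 = 0.206 at correlation 0, and 0.501 at correlation 0.5 (AR(1)). For one day it is 1.44.

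- Total-variance ratio, one day to seven: (3.24 + 1.44)/(3.24 + 0.206) = 1.358, or 4.68/3.741 = 1.251.
- Standard error inflation with share p: √(1 + p(ratio − 1)). Smallest: √(1 + 0.05 × 0.251) = 1.006. Largest: √(1 + 0.20 × 0.358) = 1.035.
- Power: Φ(2.802/inflation − 1.960) = 79.5% to 77.2%. At two-sided 10%, the level matching the planned 90% interval, Φ(2.486/inflation − 1.645) = 79.6% to 77.5%.

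A different parameterisation uses one exchangeable correlation ρ between days, with one-day to seven-day variance ratio 1/(ρ + (1 − ρ)/7). This gives 1.75, 1.35 and 1.09 for ρ of 0.5, 0.7 and 0.9. With 5% to 30% one-day values, power at two-sided 5% is 78.5% to 71.6%, 79.3% to 76.0%, and 79.8% to 78.9%. The independent-days case above corresponds to ρ = 3.24/4.68 = 0.69, so the two agree there. The 71.6% needs both noisy days (ρ = 0.5) and 30% one-day weeks.

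**The alternative rule.** In a simulation (61 per arm, 5% to 20% one-day weeks unrelated to outcome), keeping them raised the standard error 0.8% to 4.1%. Setting them to missing and relying on Weeks 1 to 3 raised it 0.6% to 7.0% as the week-to-week correlation fell from 0.9 to 0.7.

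**Responders.** Take a baseline of 6.5 and a 50% cutoff, so a score of 3.25. A true 35% reduction leaves a mean of 4.225, which is 0.975 above the cutoff. One score misclassifies it with probability Φ(−0.975/1.2) = 20.8%; the same holds for a true 65% reduction in the other direction. Seven scores misclassify 1.6% to 8.4%. The errors largely cancel across an arm: with 20% one-day weeks, the net shift in response rate is 0.2 × (−0.016 to +0.036), or −0.3 to +0.7 percentage points.

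**Bias.** Simulated true difference −0.80, week-to-week correlation 0.8, sparse weeks likelier after worsening. With 10% sparse in each arm, keeping and dropping both return −0.80. With realised shares of 14.9% (active) and 5.1% (placebo), the result depends on how far the single day sits from that subject's own weekly mean:

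| Single-day shift | Keep | Drop |
|---|---|---|
| 0 | −0.80 | −0.87 |
| +1 | −0.70 | −0.87 |
| +2 | −0.61 | −0.87 |
| −1 (extrapolated) | −0.90 | −0.87 |

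The keep column is the share difference times the shift: 0.149 − 0.051 = 0.098 per point, added to −0.80. The last row extends that line: −0.801 − 0.098 = −0.899. The drop estimate does not depend on the shift.

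A milder mechanism is drift within the week. If pain falls 0.25 to 1.0 point per week, a score from the first day of Week 4 differs from the full-week mean by 3/7 of that, or 0.11 to 0.43 point. An imbalance of 5 to 20 percentage points between arms then moves the estimate by about 0.005 to 0.09.

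**The case for a change.** The best case for acting is that the remedy is cheap and leaves the primary analysis alone: one table of diary days by week and arm, and reruns of existing models with sparse weeks set to missing or counted as non-response. If sparse weeks were unequal and informative, the stated rule could move −0.80 to −0.70 or −0.61, and nothing in the supplied text would reveal it. The conduct measures (automated review, replacement for technical loss) carry no consequence for analysis.

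Part of this stands. The textual point is correct, and a diary-day table by arm would be informative. The reruns are less useful than they appear. At a shift of 0 the stated rule is unbiased and only the drop analysis errs. At +1 the two err in opposite directions; at −1 both overshoot. They do not bracket the truth, and neither agreement nor disagreement between them shows which to believe. Counting sparse weeks as non-response would also penalise purely technical losses, and the supplied text describes no field recording why a diary day was missed.

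The −0.61 case needs a threefold imbalance and single scores averaging 2 points above the subject's own week. That is 2/1.2 = 1.67 daily SDs, about the subject's 95th percentile as an average.

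**Conclusion.** No change to the plan follows. The one-score rule is clearly stated, applies alike to both arms, and is a fair trade-off: it avoids discarding observed data at a small cost in precision that a stricter minimum would match or exceed. The 5-of-7 requirement at baseline is an eligibility condition and does not conflict with it. Automated diary review with site contact should also keep one-day weeks uncommon, although the documents do not give their frequency.

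With 5% to 20% one-day Week 4 values, expect at most about a 4% rise in the standard error and a power loss of 0.5 to 2.8 percentage points, with a response-rate shift under 1 percentage point at the 20% share. The simulation shows no bias when sparse shares are equal. These sizes rest on assumed variances and correlations, and noisier days combined with more sparse weeks would cost more power. A material bias requires informative sparse weeks, a marked imbalance between arms and a systematic shift in the single scores; the documents show none of these.

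The silence on diary-day counts is also weak evidence of a gap, because the supplied text is a brief synopsis that names no sensitivity analysis of any kind. Tabulating diary days per week by arm is sensible reporting that analysts can add without amending the plan.
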